8.5.2 Safety Analysis Population

The ASaT population will be used for the analysis of safety data in this study. The ASaT population consists of all allocated subjects who received at least 1 dose of study treatment. Subjects will be included in the treatment group corresponding to the study treatment they actually received for the analysis of safety data using the ASaT population. In this study with a single treatment regimen, the ASaT population is the same as the FAS population. For reporting consistency, the terms FAS for efficacy and ASaT for safety will be maintained.

At least 1 laboratory or vital sign measurement obtained subsequent to at least 1 dose of study treatment is required for inclusion in the analysis of each specific parameter. To assess change from baseline, a baseline measurement is also required.

Details on the approach to handling missing data for safety analyses are provided in Section 8.6 Statistical Methods.

8.6 Statistical Methods

There will be no statistical testing conducted to address the objectives of this study. A summary of the analysis strategy for efficacy variables is shown in [Table 15](#). The analysis strategy for safety is described in Section 8.6.2.

8.6.1 Statistical Methods for Efficacy Analyses

Missing Values

A missing data point for a given study visit may be due to any one of the following reasons: a visit occurred but data were not collected or were unusable; a visit did not occur; or a subject discontinued from the study before reaching the visit. Subjects who prematurely discontinued the assigned treatment are encouraged to remain in the study for follow-up, if possible.

The HCV RNA outcome is categorized as TND, TD (u), and TD (q). There are 3 types of missing data handled by different approaches.

1. Intermittent missing: If a missing data point is immediately preceded and followed by non-missing HCV RNA outcomes, the missing value would be imputed to the worst outcome of the two. For example, if a missing data point is preceded by TD(q) and followed by TD(u) or TND, then the missing value would be imputed as TD(q); if a missing data point is preceded by TD(u) and followed by TND, then the missing value would be imputed as TD(u); when a missing value is flanked by two TND, then the missing value would be imputed as TND.
2. Non-intermittent missing related to the study drug: For missing values due to premature study discontinuations due to treatment-related reasons either for safety or efficacy, the missing values will be considered as treatment failures.
3. Non-intermittent missing for reasons unrelated to the study drug: For missing data due to premature study discontinuations with reasons unrelated to treatment such as loss to follow-up, protocol deviation, withdrawal of consent, administrative reasons, etc., the missingness mechanism is unlikely to be related to subjects' response to the HCV treatment, and therefore the missing at random assumption is reasonable.

The following 2 approaches will be used to handle non-intermittent missing data due to premature discontinuations, depending on the analytical strategy, as described in the section below and in [Table 15](#).

1. Treatment-Related Discontinuation=Failure (TRD=F) approach: Subjects with treatment-related missing data (type #2 above) will be considered as failure; whereas the subjects who have the non-treatment-related missing value (type #3 above) and who do not have virologic failure during the observed study period will be excluded from the analysis for the time points following their study withdrawal. Note that subjects with documented virologic failure during the treatment or follow-up period, even if they withdrew prematurely due to reasons not related to study drug, are classified as failures.
2. Missing=Failure (M=F) approach: Subjects with any non-intermittent missing data (i.e., type #2 and #3 above) will be imputed as failures, regardless of the reason for study discontinuation.

In addition, a missing baseline/Day 1 HCV RNA result will be replaced with a screening result, if available.

Proportions of Subjects With Virologic Responses and Virologic Failures

For the primary efficacy analysis, the proportions of subjects achieving SVR₁₂ for each GT will be provided and 95% CIs for these rates will be calculated using the Clopper-Pearson method [42]. The same method will be used to analyze all binary endpoints including SVR₄, SVR₈, SVR₂₄, and virologic response rates at TW4, TW8, and end of treatment.

For the primary analyses using the FAS population, the M=F missing data approach will be utilized. In these analyses, only subjects with HCV RNA levels <LLOQ for any type of HCV infection at a given time point will be considered to have achieved the endpoint.

For all analyses conducted using the PP and mFAS populations, the missing data approach of TRD=F will be utilized. In addition, for all analyses based on these 2 populations, a subject will be considered to have achieved a response for a particular endpoint if the HCV RNA levels for the infection he/she had at baseline are <LLOQ. For example, if a subject has HCV RNA levels \geq LLOQ at a particular time point, but those RNA levels correspond to an infection that is of a different GT and/or subtype compared to the infection detected at baseline and the baseline infection has been cleared, then the subject is considered to have achieved response for the given endpoint.

To estimate the secondary efficacy endpoint of proportion of subjects experiencing virologic failure at FW12 for each GT, 95% CIs for these rates will be calculated in the mFAS analysis population using the Clopper-Pearson method [42]. The missing data approach of TRD=F described previously will be utilized for this analysis.

[Table 15](#) includes a summary of the key efficacy analyses, and [Table 16](#) includes a summary of the analysis populations and various criteria to assess the primary endpoint (SVR₁₂) and secondary endpoints (SVR₂₄ and proportion of subjects experiencing virologic failure at FW12).

Table 15 Analysis Strategy for Efficacy Variables

Endpoint/Variable (Description, Time Point)	Primary vs. Supportive Approach	Statistical Method	Analysis Population	Missing Data Approach
Primary				
Proportion of subjects achieving SVR ₁₂ by genotype	P	95% CI (Clopper-Pearson)	FAS	M=F
Proportion of subjects achieving SVR ₁₂ by genotype	S	95% CI (Clopper-Pearson)	mFAS	TRD=F
Proportion of subjects achieving SVR ₁₂ by genotype	S	95% CI (Clopper-Pearson)	PP	TRD=F
Secondary				
Proportion of subjects achieving SVR ₂₄ by genotype	P	95% CI (Clopper-Pearson)	FAS	M=F
Proportion of subjects achieving SVR ₂₄ by genotype	S	95% CI (Clopper-Pearson)	mFAS	TRD=F
Proportion of subjects achieving SVR ₂₄ by genotype	S	95% CI (Clopper-Pearson)	PP	TRD=F
Proportion of subjects experiencing virologic failure at FW12 by genotype	P	95% CI (Clopper-Pearson)	mFAS	TRD=F
CI = confidence interval; FAS = Full Analysis Set; M=F = Missing=Failure; mFAS = modified Full Analysis Set; P = primary approach; PP = Per Protocol; S = secondary approach; TRD=F = Treatment-Related Discontinuation=Failure.				

Table 16 Analysis Populations, Criteria for Response, Non-Response, and Exclusion from Analysis Populations

Analysis Population	Criteria for Response	Criteria for Non-Response	Criteria for exclusion from analysis population
FAS (Primary for SVR ₁₂ and SVR ₂₄)	HCV RNA < LLOQ	HCV RNA ≥ LLOQ	Subject did not receive at least 1 dose of study medication
PP (Supportive for SVR ₁₂ and SVR ₂₄)	HCV RNA < LLOQ for baseline infection ¹ HCV RNA ≥ LLOQ demonstrated to be due to reinfection (detectable HCV RNA for a viral strain other than that detected at baseline after clearance of baseline infection ¹)	HCV RNA ≥ LLOQ for baseline infection ¹	Subject has important deviations from the protocol including discontinuation from the study for non-treatment related reasons and other violations such as violation of inclusion/exclusion criteria and use of prohibited concomitant medications (see Section 8.5.1)
mFAS (Supportive for SVR ₁₂ , SVR ₂₄ ; Primary for the proportion of subjects experiencing virologic failure at FW12)	HCV RNA < LLOQ for baseline infection ¹ HCV RNA ≥ LLOQ demonstrated to be due to reinfection (detectable HCV RNA for a viral strain other than that detected at baseline after clearance of baseline infection ¹)	HCV RNA ≥ LLOQ for baseline infection ¹	Subject discontinued from the study for non-treatment related reasons.
FAS = Full Analysis Set; FW12 = Follow-up Week 12; GT = genotype; LLOQ = lower limit of quantification; mFAS = modified Full Analysis Set; PP = Per Protocol; RNA = ribonucleic acid; SVR ₁₂ = sustained virologic response after 12 weeks of treatment; SVR ₂₄ = sustained virologic response after 24 weeks of treatment. ¹ Baseline infection: GT(s) and subtype(s) present at baseline based on sequencing and genotyping assay			

Subject Virologic Failure: Non-response, Rebound, Virologic Breakthrough, Relapse and Reinfection

Summary statistics will be provided to describe the rates of occurrence of subject non-response, rebound, virologic breakthrough, and relapse. Definitions for subject non-response, rebound, virologic breakthrough, and relapse are in Section 4.2.5.1.1.2. Reinfection will be defined as having detectable virus of a different GT than that detected at baseline as determined by sequencing. Those with reinfection will be considered treatment success in the mFAS and PP analyses as long as HCV RNA < LLOQ is achieved for the baseline infection.

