7.1.5.5 Follow-up Visits

At the completion of study therapy, subjects will return to the study site for follow-up visits at 4, 8, 12, and 24 weeks after the last dose of study drug. Follow-up visits at 16 and 20 weeks after the last dose of study drug will be virtual visits, meaning site personnel will have telephone contact with the subject to make sure that he/she is doing well and to give a reminder for the Follow-up Week 24 visit.

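### The worst-of-two rule does not bridge consecutive missed HCV RNA visits, so a subject below LLOQ at FW4 and FW24 can be an SVR12 non-response in the FAS and has no defined SVR12 outcome in the mFAS and PP

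*Combined protocol and SAP*

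**What the plan says.** Section 8.6.1 (Missing Values) sorts missing HCV RNA into three types.

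- **Type 1, intermittent.** "If a missing data point is immediately preceded and followed by non-missing HCV RNA outcomes", the value is set to the worse of the two neighbours.
- **Type 2.** This covers "missing values due to premature study discontinuations due to treatment-related reasons either for safety or efficacy".
- **Type 3.** "For missing data due to premature study discontinuations with reasons unrelated to treatment such as loss to follow-up" and similar causes, missing at random is taken as reasonable.

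Two approaches then follow. Under Missing=Failure (M=F), every non-intermittent gap, which the text glosses as types 2 and 3, becomes a failure whatever made the subject leave. Under TRD=F, type 2 is a failure, and type 3 without virologic failure is left out for time points after study withdrawal. The populations are assigned as follows: "For the primary analyses using the FAS population, the M=F missing data approach will be utilized"; "For all analyses conducted using the PP and mFAS populations, the missing data approach of TRD=F will be utilized". On meeting an endpoint in the FAS, the text adds that "only subjects with HCV RNA levels <LLOQ for any type of HCV infection at a given time point will be considered to have achieved" it.

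On the schedule, Section 7.1.5.5 has site visits at FW4, FW8, FW12 and FW24, and says "Follow-up visits at 16 and 20 weeks after the last dose of study drug will be virtual visits", that is, telephone contacts. The blood-volume table in Section 12.3 agrees: HCV RNA is drawn in follow-up only at those four site visits.

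**The concern.** The opening of Section 8.6.1 recognises that a value can be missing because a sample was unusable or a visit did not take place, not only because the subject left the study. Yet types 2 and 3 both require study discontinuation. A subject who stays in the study is therefore covered by type 1 or by nothing, and type 1 stops working once two adjacent samples are missing.

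The primary endpoint can then disagree with a later observed result in the same subject. Section 4.2.5.1 justifies SVR12 by its high concordance with SVR24, and here a discordance would be produced by the rule alone. This is an estimation study with 25 or 50 subjects targeted per genotype, so the estimate and its interval are the result, and one subject is visible in both. The trial is also open-label with ongoing efficacy monitoring (Section 8.7). Without a stated rule, such a subject would be classified case by case with the outcome already known.

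**Working it through.** **Inputs.** The rules are those of Section 8.6.1. Samples are at end of treatment (EOT), FW4, FW8, FW12 and FW24. Target sizes are 50 for each of GT1 to GT4 (GT1 being 35 GT1a plus 15 GT1b) and 25 for each of GT5 and GT6 (Section 8.9.1). Intervals are two-sided 95% Clopper-Pearson.

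**Step 1: reproduce the plan's own figures.** For x responders out of n, the lower limit is the 0.025 quantile of Beta(x, n−x+1) and the upper limit is the 0.975 quantile of Beta(x+1, n−x). For x=n the upper limit is 100%. For 49/50 this gives 98.0% (89.4, 99.9), as in Table 18. All 16 rows of Table 18 reproduce to one decimal.

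**Step 2: apply the rules to every visit pattern.** Take EOT as observed and every observed value as below LLOQ. The four follow-up visits give 2⁴ = 16 patterns, of which 8 have FW12 missing:

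| Missing visits | FW12 under Section 8.6.1 | FAS SVR12 | FAS SVR24 |
|---|---|---|---|
| FW12 | Type 1 | success | success |
| FW4, FW12 | Type 1 (FW8 and FW24 observed) | success | success |
| FW8, FW12 | no type fits | non-response | success |
| FW4, FW8, FW12 | no type fits | non-response | success |
| FW12 and FW24, with or without FW4 and FW8 (4 patterns) | Type 2 or 3 if discontinued; otherwise no type | non-response | non-response |

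Rows 3 and 4 are the problem. FW12 has no result directly before it, so type 1 fails. The subject attends FW24, so has not discontinued, and types 2 and 3 fail. In the FAS, the responder rule requires a value below LLOQ at the time point and there is none, observed or imputed. That, with the general M=F principle, makes SVR12 a non-response. Row 1 differs from row 3 only by the FW8 sample, with the same FW24 result, and is a success.

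**Step 3: mFAS and PP.** TRD=F fails type 2 and removes type 3 only after withdrawal. Neither applies. The mFAS excludes only for study discontinuation, so the subject stays in that denominator without an SVR12 outcome.

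**Step 4: size in the FAS.** One subject moves the estimate by 100/n: 100/50 = 2.0 points, 100/25 = 4.0 points, and in the GT1 subtypes 100/35 = 2.9 and 100/15 = 6.7 points.

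| n | Otherwise | With one such subject |
|---|---|---|
| 50 | 50/50 = 100% (92.9, 100) | 49/50 = 98.0% (89.4, 99.9) |
| 50 | 49/50 = 98.0% (89.4, 99.9) | 48/50 = 96.0% (86.3, 99.5) |
| 25 | 25/25 = 100% (86.3, 100) | 24/25 = 96.0% (79.6, 99.9) |
| 25 | 24/25 = 96.0% (79.6, 99.9) | 23/25 = 92.0% (74.0, 99.0) |

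Two such subjects, with all others responding, give 96.0% (86.3, 99.5) at n=50 and 92.0% (74.0, 99.0) at n=25. Each subject costs one row of Table 18.

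**The case against.** **The text may intend a two-way split.** On this reading, a gap with later data is intermittent and dropout is non-intermittent. The worked examples under type 1 speak more loosely of results on either side, without repeating *immediately*. FW8 and FW12 would then be bridged by FW4 and FW24. This may well be the intention, but the operative sentence says *immediately*, and a programmer following it would not bridge the gap.

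**The plan never says that this subject fails.** This is largely right. A reader might infer that the plan scores the subject an SVR12 failure in every analysis. It does not: M=F is spelled out as types 2 and 3 only, and Table 16 reserves FAS non-response for values at or above LLOQ, which this subject never had in follow-up. Non-response in the FAS rests on the responder rule and the general M=F principle. In the mFAS and PP the outcome is undefined. Section 8.5.1 also removes administrative non-virologic failures from the PP, but using that here would presuppose the failure score and would discard the SVR24 success too.

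**The effect is small.** This stands. The pattern needs two consecutive lost samples, despite windows of two weeks either side, and then a return at FW24. There is no hypothesis test to cross. The error lowers SVR12, the direction expected of a Missing=Failure analysis.

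**Sections 8.0 and 8.6.3 provide for a supplemental SAP.** That is a route for the correction. The topics assigned to it in Section 8.6.3 (baseline summaries, PK and exploratory endpoints) do not include this one.

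**Conclusion.** The point holds in a limited form. Type 1 does not bridge two or more consecutive missing HCV RNA visits, even with results on both sides. In the primary FAS analysis the outcome is an SVR12 non-response beside an SVR24 response; in the mFAS and PP no SVR12 outcome is assigned. The cost in the FAS is 2.0 points per subject at n=50 and 4.0 at n=25. How often this happens is not in the documents; 0 to 2 per genotype is an assumption, and at zero nothing changes.

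Three stronger inferences are not supported. The rule is not confined to one missed visit per subject, because FW4 and FW12 can both be missing and each is bridged when FW8 is present. The subject is not a virologic failure, so neither the secondary virologic-failure endpoint nor the efficacy stopping criteria in Section 5.11.4 count this subject as one. And SVR12 is not inflated: the FAS error is conservative.

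It is still worth correcting before database lock. Following the stated primary rule gives a result that the trial's own later observation contradicts, and the remedy is almost free.

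**What to change.** Keep type 1 and its worst-of-two imputation. Reword the condition so that it covers a gap of any length, bounded by the last non-missing HCV RNA result before it and the first non-missing result after it. For the subject above, FW12 takes the worse of FW4 and FW24, both below LLOQ, and SVR12 is achieved. Leave the reinfection rule for the mFAS and PP (Section 8.6.1 and Table 16) in force.

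Add two sentences. The first should say that M=F in the FAS also applies to subjects still in the study with no HCV RNA result at or after FW12. The second should say how TRD=F treats them in the mFAS and PP.

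Replacing type 1 by a rule that simply takes the next available result would be a poorer choice. It would drop worst-of-two. If any earlier post-treatment value at or above LLOQ ruled out SVR12, an unconfirmed value would count as failure, although Section 4.2.5.1.1.2 requires confirmation for relapse. It would also override the reinfection rule unless an exception were written in.

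The cost is a few lines of text in the supplemental SAP, which Section 8.0 allows before final database lock, and a small programming change. No new data are needed.

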- **Relapse:** Subject has a confirmed HCV RNA \geq LLOQ [TD(q)] following end of all study therapy, after becoming undetectable (target not detected [TND]) at end of treatment. Confirmation is defined as an HCV RNA \geq LLOQ from a separate blood draw repeated within 2 weeks.

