7.1.3.2.2 Pharmacodynamics: Viral Kinetics

HCV RNA samples also will be collected at the Week 1, 2, 4, 6, 8, 10 and 12 visits for all subjects during treatment (and Week 14 and 16 visits for subjects whose treatment duration may be extended). Additional samples for HCV RNA will be collected on a subset of subjects in the Intensive PK/PD group (see [Table 13](#)). The data from this sub-study will be used to validate the existing viral dynamics model for MK-3682 and RZR. A total of approximately 30 subjects, the first 5 subjects for each GT1-6 who consent to participate, will undergo additional PK and PD evaluations and have electrocardiographs (ECGs) performed.

See Section 6.0 Trial Flow Chart and [Table 13](#) for detailed information on sample collection and visits.

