8.7 Interim Analyses

An assessment of safety for the first 50 subjects will be made when the last of these subjects reaches TW4. The criteria for assessing safety in this cohort of 50 subjects can be found in

Section 5.11.1. Specifically, if >3 out of the first 50 subjects receiving MK-3682 + RZR experience any of the listed criteria, study therapy will be discontinued in all subjects and no additional subjects will be allocated to treatment.

In addition to the safety assessment for the first 50 subjects, criteria for early stopping at any point in the trial is given in Section 5.11.2 and for pausing treatment allocation is given in Section 5.11.3.

An assessment of efficacy will be made when the first 10 per-protocol subjects within each GT (GT1-6) have reached FW4. If ≥ 3 out of the first 10 subjects in the PP population for each GT (GT1-6) receiving 12 weeks of therapy experience virologic failure (non-response, rebound, breakthrough, or relapse) by FW4, no additional subjects for that particular GT will be allocated to treatment in the trial. Additionally, if the majority of failures are due to relapses (i.e., $>50\%$), the treatment regimen with MK-3682 + RZR for subjects with a particular GT will be extended to 16 weeks' duration and RBV will be added for subjects with this GT who remain on treatment.

In addition, efficacy will continue to be monitored throughout the trial and if >5 of subjects in the PP population for GT1-4, and >3 subjects in the PP population for GT5-6, experience virologic failure at any point in the trial, no additional subjects for that particular GT will be allocated to treatment. Additionally, if the majority of failures are due to relapses (i.e., $>50\%$), the treatment regimen with MK-3682 + RZR for subjects with a particular GT will be extended to 16 weeks' duration and RBV will be added for subjects with this GT who remain on treatment.

Finally, throughout the course of this open-label study, efficacy and safety will be monitored for trends and programmatic decisions.

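### The worst-of-neighbours imputation in 8.6.1 does not stop at the end of treatment, so a relapse already detectable at FW4 can overwrite a missing end-of-treatment result

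*Combined protocol and SAP*

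**What the plan says.** The combined protocol and SAP, Section 8.6.1 (Missing Values), introduces its rules visit by visit: "A missing data point for a given study visit may be due to any one of the following reasons". The first type, intermittent missing, covers a gap with an observed result on each side, and for it "the missing value would be imputed to the worst outcome of the two". The categories run from TND (best) through TD(u) to TD(q) (worst). The worked examples show only a preceding value as bad as or worse than the following one, so the general sentence governs the reverse order.

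HCV RNA samples are "collected at the Week 1, 2, 4, 6, 8, 10 and 12 visits for all subjects during treatment" (Section 7.1.3.2.2). The next scheduled draw is FW4 (Sections 6.0 and 7.1.5.5).

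Three parts of the plan use end-of-treatment status or the failure type:

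- Section 4.2.5.1.1.2 counts a confirmed quantifiable result after therapy as relapse only "after becoming undetectable (target not detected [TND]) at end of treatment".
- Section 8.6.1 includes "virologic response rates at TW4, TW8, and end of treatment" among the binary endpoints. It also promises summary rates for each failure type.
- Sections 5.11.4 and 8.7 ask, once a failure-count criterion is met for a genotype, "if the majority of failures are due to relapses", meaning more than 50%.

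**The concern.** The rule is conservative while both neighbours lie in the same period. At the end of treatment they do not: one neighbour is on drug and the other is off drug. A result at FW4 carries little information about viral suppression at TW12, because relapse by definition occurs after therapy stops. Writing the FW4 value back into TW12 makes a post-treatment event look like an on-treatment one.

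At stake are end-of-treatment response and the relapse rate, both reported in small genotype groups where one subject is visible. The distinction between on-treatment failure and relapse is also one the plan itself relies on when it describes how the regimen failed.

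**Working it through.** **Inputs.** Neighbours of TW12: TW10 and FW4 (7.1.3.2.2, 7.1.5.5). For a subject extended to 16 weeks, the same position is TW16, between TW14 and FW4. Group sizes: 50 for each of GT1 to GT4 and 25 for each of GT5 and GT6 (Table 1). Response means HCV RNA below LLOQ; TD(u) is below LLOQ and TD(q) is not (Table 5).

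**Step 1: apply the rule with TW12 missing and TW10 TND.**

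| FW4 | Imputed TW12 | End-of-treatment response | TND condition for relapse |
|---|---|---|---|
| TND | TND | yes | met |
| TD(u) | TD(u) | yes | not met |
| TD(q) | TD(q) | no | not met |

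If TW10 were carried forward, TW12 would be TND in all three rows and the condition would be met. A relapse first seen at FW8 or later, with TND at TW10 and FW4, is in the first row and keeps its label.

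**Step 2: test the third row against the other definitions in 4.2.5.1.1.2.**

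- Non-response is not met, because the subject was below LLOQ on treatment.
- Rebound is not met, because an imputed category gives no log10 rise and no confirming on-treatment draw.
- Breakthrough is not met, because an imputed value has no separate confirming draw.

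The subject fits none of the four types.

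**Step 3: size for end-of-treatment response.** One subject is 1/50 = 2 points or 1/25 = 4 points. No figure in the plan depends on the imputation rule, but Table 18 gives the exact intervals at these sizes, and its Clopper-Pearson values reproduce. At n=50, 50/50 (92.9, 100.0) becomes 49/50 (89.4, 99.9). At n=25, 25/25 (86.3, 100.0) becomes 24/25 (79.6, 99.9).

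**Step 4: likelihood.** The plan gives no rate for missing TW12 samples. Take m = 2% to 5% as an assumption, with samples missing independently. The chance that at least one of four relapses lacks TW12 is 1 − (1 − m)^4:

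- m = 2%: 1 − 0.98^4 = 0.078, or 8%
- m = 5%: 1 − 0.95^4 = 0.185, or 19%

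These are upper values, because the relapse must also be detectable at FW4.

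**Step 5: relapse share, only if monitoring were to use imputed values.** Suppose 4 of 6 failures in one of GT1 to GT4 are relapses (67%, a majority).

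- One relapse recoded to another type: 3/6 = 50%, not a majority.
- One relapse dropped from the failures: 3/5 = 60%, still a majority, but five failures no longer meet the criterion of more than five.

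**The case against.** The strongest reply is that failure typing was never meant to use imputed values. Rebound, breakthrough and relapse all require confirmation from a separate blood draw, and Sections 5.11.4 and 8.7 do not invoke the imputation rule. This is a fair reading, and it means no effect on the regimen-modification rule is shown. It does not settle the point. End-of-treatment response is analysed in 8.6.1 itself, under that section's missing-data rules. With observed data only, TW12 is simply absent, and the TND that relapse requires is still not established.

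A second reply is that end of treatment could mean the last on-treatment sample, in which case the example stays a relapse. The text allows this but does not say it.

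A third is that a confirmed quantifiable FW4 result remains a failure whatever it is called. Section 8.6.1 keeps documented virologic failures as failures, and Table 16 treats a result at or above LLOQ for the baseline infection as non-response in the mFAS. This stands: loss from the FW12 virologic-failure count is possible but not shown.

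Finally, little depends on it. End-of-treatment response is exploratory (8.4.1.3), with details of exploratory analyses left to the sSAP (8.6.3). Failure types receive summary statistics only, and nothing is tested. This limits the weight of the point, not its correctness.

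**Conclusion.** The concern holds in a limited form. As written, the rule lets an FW4 result set a missing end-of-treatment value. Each subject who is TND at the last on-treatment draw and quantifiable at FW4 costs 2 points of end-of-treatment response at n=50 or 4 points at n=25. On a literal reading, that subject also loses the relapse label and gains no other. With FW4 at TD(u), only the relapse condition is affected.

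Three stronger readings are tempting, and the documents do not support them:

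- *Every relapser without a TW12 sample is misclassified.* Only those already detectable at FW4 are.
- *True relapses leave the virologic-failure endpoint.* The provisions on documented failures and Table 16 may keep them in.
- *The rule changes who has the regimen modified.* That requires monitoring to use imputed values, which no section states. The counts also matter: with six relapses among six failures, the chance of at least one missing TW12 is higher (1 − 0.98^6 = 11% to 1 − 0.95^6 = 26%), but one reclassification leaves 5/6 = 83%, still a majority. The change from 67% to 50% needs four of six, for which 8-19% is the upper range.

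SVR12 and SVR24 are unaffected. All the probabilities rest on the assumed 2-5% missing rate. The change is worth making because the rule gives a wrong result as stated and is cheap to correct.

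**What to change.** Add to the first missing-data type in Section 8.6.1: *Post-treatment results are not used to impute an on-treatment or end-of-treatment value; if the end-of-treatment sample is missing, the last observed on-treatment HCV RNA result is used.* Leave the worst-of-two rule as it is within treatment and within follow-up. Also state that virologic-failure types and the counts in Sections 5.11.4 and 8.7 use observed, confirmed results.

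The cost is two sentences and one programming condition, which the supplemental SAP can carry before database lock (Section 8.0). The downside is small: end-of-treatment status may rest on a sample about 2 weeks older. No change to the clinical rule is proposed.

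### The primary FAS rule scores SVR12 and SVR24 on the visit HCV RNA alone, so a virologic failure who clears virus on non-study HCV therapy counts as a success of the study regimen

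*Combined protocol and SAP*

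**What the plan says.** **FAS (primary for SVR12 and SVR24).** Section 4.2.5.1.1.1 defines each endpoint by one HCV RNA result below the LLOQ, 12 or 24 weeks after study therapy ends. Section 8.6.1 adds that "only subjects with HCV RNA levels <LLOQ for any type of HCV infection at a given time point will be considered to have achieved" SVR. The FAS row of Table 16 gives a result below the LLOQ as response and a result at or above it as non-response, and lists nothing else. Its only exclusion is "Subject did not receive at least 1 dose of study medication". The missing-data rule for this set is M=F: "Subjects with any non-intermittent missing data (i.e., type #2 and #3 above) will be imputed as failures".

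**mFAS and PP (supportive for SVR).** The missing-data rule is TRD=F. A note under it says that "subjects with documented virologic failure during the treatment or follow-up period, even if they withdrew prematurely due to reasons not related to study drug" count as failures. Section 8.6.1 then says a subject has achieved "a response for a particular endpoint if the HCV RNA levels for the infection he/she had at baseline are <LLOQ", and Table 16 repeats this as "HCV RNA < LLOQ for baseline infection".

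**Follow-up and other therapy.** Section 5.5 prohibits non-study HCV therapy through FW24 and requires any use to be reported. Section 7.1.5.6 keeps relapsers in their remaining follow-up visits and follows on-treatment failures for 24 weeks after confirmation. No FAS rule says how a result obtained after non-study therapy is scored.

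**The concern.** The primary objective is the efficacy of MK-3682 + RZR. A subject who fails that regimen, is treated with something else and is then below the LLOQ says nothing in its favour. Yet the stated FAS rule scores that subject as a responder, because the value is observed and below the threshold. M=F does not apply, since nothing is missing.

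The error runs in one direction: it can only raise the SVR rate. It also allows contradictory reporting. The same subject could be a success for SVR12 in FAS and a virologic failure in the FW12 failure endpoint in mFAS. With genotype groups of 25 or 50, one subject is visible in the reported rate.

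**Working it through.** **Step 1: can the case arise?** Each link comes from the protocol.

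- The subject relapses. Section 4.2.5.1.1.2 requires confirmation by a second draw within 2 weeks.
- The subject remains in follow-up (Section 7.1.5.6).
- The subject takes non-study HCV therapy. This is a deviation, but Section 5.5 foresees that it may be reported.
- The subject is not removed from the trial. The first row of Table 11 allows removal on the judgement of the investigator or sponsor. The non-compliance row favours continued monitoring.
- The SVR visit is timed from the end of study therapy, so other therapy does not move it.

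If the subject is removed, later values are missing and M=F scores a failure. The gap exists only for subjects who stay.

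**Step 2: timing, at nominal visits.** Take a relapse seen at FW4.

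- Confirmed by FW4 + 2 = FW6.
- Time left to SVR12: 12 − 6 = 6 weeks. Time left to SVR24: 24 − 6 = 18 weeks.
- An assumed 12-week course from FW6 ends at FW18. It is half done at FW12 and 24 − 18 = 6 weeks past its end at FW24.

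SVR24 is therefore the more exposed endpoint. SVR12 is not immune, because the rule asks only for a value below the LLOQ and not for a finished course. As an illustration, Table 4 shows 85/92 prior DAA failures below 15 IU/mL at Treatment Week 4 and 92/92 at Week 8 on an investigational three-drug regimen. The assay's LLOQ is 15 IU/mL (Section 7.1.3.3).

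**Step 3: size.** The interval is the two-sided 95% Clopper-Pearson interval named in Section 8.6.1:

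- lower = Beta quantile (0.025; x, n − x + 1)
- upper = Beta quantile (0.975; x + 1, n − x)

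All 16 rows of Table 18 reproduce to one decimal. Group sizes are the targets in Section 8.9.1: 50 for each of GT1 (35 + 15), GT2, GT3 and GT4, and 25 for each of GT5 and GT6. The numbers of failures and of re-treated failures below are assumptions, because the documents give none. The range runs from no failure re-treated to all of them.

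| n | Failures | Re-treated and <LLOQ at visit | Scored SVR | 95% CI |
|---|---|---|---|---|
| 50 | 3 | 0 | 47/50 = 94.0% | 83.5 to 98.7 |
| 50 | 3 | 1 | 48/50 = 96.0% | 86.3 to 99.5 |
| 50 | 3 | 2 | 49/50 = 98.0% | 89.4 to 99.9 |
| 50 | 3 | 3 | 50/50 = 100% | 92.9 to 100 |
| 25 | 2 | 0 | 23/25 = 92.0% | 74.0 to 99.0 |
| 25 | 2 | 1 | 24/25 = 96.0% | 79.6 to 99.9 |
| 25 | 2 | 2 | 25/25 = 100% | 86.3 to 100 |

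One such subject adds 1/50 = 2.0 points or 1/25 = 4.0 points. In these examples the first one raises the lower bound by 86.3 − 83.5 = 2.8 points (n=50) or 79.6 − 74.0 = 5.6 points (n=25).

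**The case against.** **The quoted FAS sentence states a necessary condition.** It says that only subjects below the LLOQ qualify, and its purpose is to deny FAS any credit for reinfection. That is right as far as the sentence goes. But Section 4.2.5.1.1.1 and the FAS row of Table 16 give the visit value as the whole criterion, so the literal reading stands.

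**The case needs a chain of events.** The subject must fail, break the prohibition, not be removed, keep attending and be below the LLOQ. This stands: the number may well be zero.

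**Little depends on it.** There are no hypothesis tests. The stopping rules in Section 5.11.4 count virologic failures, not SVR. Failure through FW12 is a separate endpoint, and relapse rates are summarised. This also stands and keeps the point minor.

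**A supplemental SAP is foreseen in Section 8.0.** It may settle the matter. It is not among the documents, so this cannot be checked.

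A reader might also infer more than the text supports:

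- *That mFAS and PP have the same gap.* The TRD=F note sits under a passage introduced with "The following 2 approaches will be used to handle non-intermittent missing data due to premature discontinuations, depending on the analytical strategy", and the response rule that follows has no exception for earlier failure. But the words about premature withdrawal extend the note to withdrawers; they do not confine it to them. The only example given for the baseline-infection rule is a different genotype or subtype, so its purpose is to separate reinfection from failure. Read together, documented failures are already failures in these sets.
- *That PP would drop the subject.* Table 16 lists "use of prohibited concomitant medications" but refers to Section 8.5.1. That section limits this violation to drugs that lower MK-3682 or RZR concentrations, and it drops data after deviations during treatment. HCV therapy started after study treatment fits neither. Only the open-ended clause on other violations could reach it.

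**Conclusion.** The point holds for FAS and is minor. As written, the primary rule credits the study regimen with a response obtained on other HCV therapy after virologic failure. Each such subject adds 2 points to a genotype's rate at n=50 or 4 points at n=25, and the bias can only be upward. SVR24 is the more plausible place for it; SVR12 is possible but has less time.

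The size per subject rests only on the target group sizes. How many subjects are affected cannot be derived, because the documents give no rate of non-study therapy. A reader might infer that at least one case is likely somewhere among about 250 subjects. That would rest on assumed failure and re-treatment rates pooled over the whole trial, whereas SVR is estimated by genotype. Nor do the documents show that mFAS or PP would score the subject wrongly; a confirming cross-reference is enough there.

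**What to change.** Add to Section 8.6.1, or to the supplemental SAP before database lock, and align the FAS row of Table 16:

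> In FAS, a subject who starts any non-study HCV therapy before the endpoint visit is a non-responder at that and all later visits, regardless of later HCV RNA. In mFAS and PP, a documented virologic failure (Section 4.2.5.1.1.2) remains a failure regardless of later non-study therapy; a subject whose baseline infection cleared and whose non-study therapy was for sequencing-confirmed reinfection keeps the existing reinfection rule.

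The FAS sentence is tied to the start of other therapy for two reasons. Carrying every confirmed failure forward, with or without other therapy, would go further than the problem requires. And relapse requires target not detected at end of treatment, so a subject who is detected but unquantifiable then and later reaches the LLOQ may meet no failure definition; a rule tied to therapy still catches that subject if re-treated. The reinfection clause is needed because, after successful treatment of a reinfection, no quantifiable RNA is left at the visit to show what it was.

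The cost is two sentences and one table row. Failure confirmation visits and non-study HCV therapy are already recorded.
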